### **Additional descriptive analyses in the presence of missing data**

The number of participants who prematurely discontinue the study and study intervention for any reason, as well as the reasons for premature discontinuation of study and study intervention will be reported.

All dropouts will be carefully evaluated with respect to baseline characteristics. If necessary, additional sensitivity analyses may be performed.

## **4.3.2 COVID-19 pandemic-related missing data**

### **4.3.2.1 Efficacy Variables**

Data collected during an active COVID-19 infection (confirmed by a positive SARS-CoV-2 test by PCR or a positive serology IgG test or an AE confirming COVID-19 infection) will be discarded from the analysis as they are expected to be biased (see Section 4.5.3).

Treatment interruptions and additional pandemic-related reasons for treatment interruption will be collected and the time of the interruption will be subtracted from the exposure duration (for details see Section 6.4.2).

The number of participants who prematurely discontinue the study and study intervention for any pandemic-related reason, as well as the reasons for premature discontinuation of study and study intervention will be reported.

The number of subjects with missed visits and the number of subjects with missed cough count key assessments due to COVID-19 pandemic will be displayed as well as the reason why the visit/ assessment was not performed.

### **4.3.2.2 Safety Data**

All available safety data will be reported without any imputations besides the ones described in Section 4.3.1.2.

## **4.4 Interim Analyses and Data Monitoring**

Not applicable.

## **4.5 Data Rules**

### **4.5.1 Definition of Baseline**

Baseline values for descriptive statistics and model-based analyses will be determined as the last non-missing values before the start of treatment.

#### 4.5.2 Handling of Repeated Measurements

If more than one measurement is available at screening (e.g. for laboratory), the last observation of those will be used for descriptive statistics tables as well as for frequency tables. In case of repeated measurements at planned time points after intake of study medication, the earliest measured value will be used for descriptive statistics tables as well as for frequency tables.

#### 4.5.3 Data Rules in case of COVID-19 infection

Efficacy data collected from the start of an active COVID-19 infection until the end of the study will be discarded for the primary analysis. The start of an active COVID-19 infection is defined as the date of the first positive SARS-CoV-2 test or the first positive serology IgG test or the start date of the AE confirming the COVID-19 infection, whichever is earliest.

The relevant MedDRA preferred terms are:

- PT: COVID-19
- PT: COVID-19 pneumonia
- PT: Coronavirus infection
- PT: Asymptomatic COVID-19
- PT: Coronavirus test positive
- PT: Exposure to SARS-CoV-2
- PT: Occupational exposure to SARS-CoV-2
- PT: Middle East respiratory syndrome
- PT: Severe acute respiratory syndrome
- PT: Suspected COVID-19
- PT: COVID-19 treatment
- PT: SARS-CoV-2 test false negative
- PT: SARS-CoV-2 test positive
- PT: SARS-CoV-2 test false positive
- PT: SARS-CoV-2 antibody test positive
- PT: SARS-CoV-2 carrier
- PT: SARS-CoV-2 sepsis
- PT: SARS-CoV-2 viraemia

see Appendix 3 [2].

Sensitivity analyses with inclusion of all available data will be performed for the primary and secondary efficacy endpoint (for details see Sections 6.2.1.3.2 and 6.2.2 ).

The distinguishment of P2X3 related taste AEs from COVID-19 related smell/taste symptoms will be done by medical review based on the details of smell/taste disturbance assessments, the SARS-CoV-2 test results, the AEs confirming COVID-19 and the timing information.

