#### Intercurrent events:

- a) Early discontinuation of study or study intervention for any reason: use data until discontinuation (while on treatment strategy). For handling the intercurrent event (ICE) of early discontinuation of the study and of the study intervention the while on treatment strategy will be applied. This strategy considers measurements of the endpoint up until the time of the intercurrent event. The last observation of the endpoint prior to the event will be used in the analysis. LOCF for all missing data due to early discontinuation will be applied.
- b) Non-compliance with study intervention: use data during compliant periods (while on treatment strategy) on a visit-by-visit approach:  
compliance will be calculated for the period between two consecutive visits. If the compliance is too low (i.e. below 80%), or too high (i.e. >120%, which is highly unlikely) the data collected during this period and the subsequent visit will not be used. Instead, the mean value of the observations between the adjacent compliant

visits (i.e. end point of the preceding compliant period and end point of the following compliant period) is taken. If there is no following period that can be used, LOCF will be applied. If there is no preceding compliant period, the mean value of the baseline value and the observation of the end of the first compliant period will be used.

- c) COVID-19 infection: use data prior to an active COVID-19 infection which is defined as the date of the first positive SARS-CoV-2 test or the date of the first positive serology IgG test or the start date of the AE confirming a COVID-19 infection (while on treatment), whichever is earliest. Symptoms of an acute COVID-19 infection are expected to have a major impact on the primary endpoint. Since long term effect of such an infection is unknown, only the data prior to the intercurrent event of an active COVID-19 infection will be used. LOCF imputation will be used in this case.

The **population** the primary estimand bases on is the population as described by the inclusion/exclusion criteria given in section 5 of the CSP and further by the PPS analysis population in section 5.1.

The **population-level summary** is the estimated geometric mean ratio (relative to baseline) of the primary efficacy variable by intervention group.

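### SAP 4.5.3 starts the COVID-19 discard rule from a confirming adverse event, but its term list includes exposure, suspected and false-positive terms, and no text says which terms count

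*SAP*

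**What the plan says.** SAP 4.5.3 sets the rule: "Efficacy data collected from the start of an active COVID-19 infection until the end of the study will be discarded for the primary analysis". It applies from the earliest of three dates: the first positive SARS-CoV-2 test, the first positive IgG serology, or "the start date of the AE confirming the COVID-19 infection, whichever is earliest". For the primary variable, intercurrent event c) in SAP 6.2.1 adds that "LOCF imputation will be used in this case".

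Straight after the rule, 4.5.3 continues "The relevant MedDRA preferred terms are" and lists 18 terms. Among them are "PT: Exposure to SARS-CoV-2", "PT: Occupational exposure to SARS-CoV-2", "PT: Suspected COVID-19" and "PT: SARS-CoV-2 test false positive". The list closes with a pointer to an appendix of a company COVID-19 document (SAP reference [2]), which is not part of the protocol or SAP.

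**The concern.** The adverse-event date acts alone: no supporting test is required. What counts as such an event therefore decides whose cough counts are kept in the primary analysis. The SAP gives one list of terms, and four of its entries do not fit the word that defines the trigger. A programmer who builds the flag from the list and a programmer who first removes the non-confirming terms would produce different primary data sets from the same text. The affected data would be valid 24-hour recordings from people who were never infected, discarded on the ground that infection distorts cough.

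**Working it through.** The plan states no figure on this point, so the check is a reading of the passages against each other.

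**1. The list.** It has 18 terms. Two record exposure, one records suspicion and one records a test result judged wrong. That is 4 of 18 terms (4/18 = 22%). This is a share of terms, not of participants.

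**2. Is a filter stated anywhere?**

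- SAP 4.3.2.1, 6.2.1 c) and 6.2.1.3.2 item 1 all refer to an adverse event confirming COVID-19. None names a subset of terms, asks for a supporting test or provides for adjudication.
- SAP 4.5.3 and 6.4.1.1 provide medical review, but only to separate drug-related from COVID-related taste and smell events. In that review the confirming adverse events are an input.
- SAP 4.6 monitors positive tests and the outcomes of confirming adverse events, and allows a documented change to the analysis after data review. It does not classify terms.
- SAP 5.1 settles assignment to analysis sets, not this trigger.
- SAP 6.1.1 uses a broader notion, a COVID-19 adverse event, for descriptive subgroups. The SAP thus works with two concepts but prints one list.

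**3. What the two readings do.** Recordings fall nominally on days 14, 28, 56 and 83 (protocol Schedule of Activities). Take participants with an exposure adverse event.

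| Case | All listed terms trigger | Only confirming terms trigger |
|---|---|---|
| Never infected; event between days 28 and 56 | Week 8 and week 12 counts discarded; week 4 count stands in for week 12; classed as infected if the split uses the list | All counts kept; week 12 count used; classed as uninfected |
| Never infected; event before day 14 | No post-baseline count survives; leaves the per-protocol set under SAP 5.1 if discarded counts are treated as missing | Stays in with all counts |
| Event between days 14 and 28, then a positive test between days 56 and 83 | Only the week 2 count survives and is carried forward | Counts to week 8 survive; week 8 is carried forward |

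The third case follows from the earliest-date rule: a non-confirming term can also move the cut-off forward in someone who is infected later.

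**4. The false-positive term.** Deleting it does not close the gap by itself. The result behind it may already count as a first positive test, and the SAP does not say whether a test later documented as false positive still counts.

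**5. Size.** Neither document gives an expected frequency for these terms. Protocol 10.3.1 defines an adverse event as an untoward medical occurrence and sets aside situations in which none occurred, so bare exposure should seldom be recorded as one. The number affected is probably very small, but it cannot be calculated.

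**The case against.** The strongest reply is that the word confirming already does the filtering. The rule concerns an active infection and an adverse event that confirms it. An exposure, a suspicion or a false-positive test confirms nothing. The list is headed only as relevant terms, SAP section 7 describes it in the same way, and its mixed content looks like a broad search list. The cited company appendix may separate the terms. Testing is planned during the study (protocol 2.3.3.7 and 8.2.5), so for many true infections a test will supply or support the date. Analyses that keep all data are planned for the primary endpoint on both analysis sets (SAP 6.2.1.3.2 items 2 and 3) and for every secondary and exploratory endpoint on the per-protocol set (6.2.2 and 6.2.3, item 3 of each).

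Much of this stands. A reader might infer that the SAP orders all 18 terms to start the discard. The documents do not support that: the wording allows the filtered reading, and the appendix cannot be checked. What remains is that the list follows the trigger directly, is the only operational content given for it, and carries no stated filter. The all-data analyses limit the consequences, but they do not define the primary data set or correct the infected/uninfected split.

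**Conclusion.** The point holds as a minor defect of specification in a rule that shapes the primary variable. Applied as the trigger, the list discards valid cough counts of uninfected participants and misclassifies the split in 6.2.1.3.2 item 1. The second consequence assumes that the split uses the same list, which the SAP does not state. If a filter is intended, it is not written down.

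Two stronger conclusions should not be drawn. A reader might infer a loss of power, but any such figure would need a frequency that the documents do not give; none is claimed, and the direction of any bias is unknown. A reader might also infer that carried-forward values enter the Leicester Cough Questionnaire and cough severity analyses. SAP 6.2.2 refers those endpoints to the same intercurrent-event handling, but 6.2.2.2 analyses their change scores with a repeated-measures model under missing at random. The text does not settle this, and the point does not rest on it.

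**What to change.** Before unblinding, and for the intercurrent-event trigger only:

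- Remove "PT: Exposure to SARS-CoV-2", "PT: Occupational exposure to SARS-CoV-2" and "PT: SARS-CoV-2 test false positive" from the terms that start the event.
- State that a positive test documented as false positive does not start it.
- Let "PT: Suspected COVID-19" start it only if a positive test supports it or infection is confirmed at the blinded data review already planned in SAP 4.6.
- Use the resulting flag in both 6.2.1 c) and 6.2.1.3.2 item 1.

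The full list may stay for listings and for the descriptive COVID-19 subgroups in 6.1.1. The cost is a few sentences in the SAP and a blinded look at any flagged cases. No new data are needed, and the planned sensitivity analyses stay as they are.

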#### **4.5.4 Twenty-four-hour cough recording**

24h-cough recordings with less than 20 hours of valid cough recording will be excluded from the primary analysis. A sensitivity analysis including all available cough count data will be performed.

#### **4.5.5 Cough Severity VAS and SCCD**

VAS and SCCD are collected on a daily basis from Visit 1 until the Safety Follow-up Visit.

The baseline value is calculated as the average of the 14 days up to and including Visit 2, i.e. the average of day -13 up to day 0.

The value at a post-baseline visit is calculated analogously as the average of the 14 days up to and including the respective visit.

If there are less than 14 days between consecutive visits, the average will only be taken over the days between the visits and including the respective visit.

If there are less than 8 out of 14 days available, the value will be set to missing [3]. The VAS reported for the day of Visit 1 will not be considered at all for statistical analyses, as it has a different recall period.

For the SCCD item-levelscore calculation rules see Psychometric SAP v3.0. [4]. Missing data will not be imputed.

#### **4.5.6 Unscheduled Visits and Safety Follow-up (SFU)**

Data from unscheduled visits will generally not be considered for descriptive tables with the exception of laboratory parameters see section 6.4.3 and 6.4.4. For the compliance calculation data from unscheduled visits will be used see section 6.4.2. The data from unscheduled visits will be displayed in the listings in Appendix 16 of CSR.

For cough severity VAS, PGI-S/C, EQ-5D-5L and LCQ, an extra line showing Safety follow-up (SFU) data will be added to the respective descriptive tables of the intervention period.

#### **4.5.7 Definition of Region**

Subjects will be stratified for randomization according to geographic region

- Japan,
- Europe (Belgium, Czech Republic, France, Germany, Hungary, Italy, Netherlands, Poland, Slovakia, Spain, United Kingdom),
- ROW (Argentina, Australia, Canada, Russian Federation, Taiwan, Turkey, United States).

#### **4.5.8 Definition of Treatment-emergence**

A treatment-emergent AE is defined as any event arising or worsening after the start of study drug administration until 14 days after the last study medication intake.

#### **4.5.9 Data Rules for laboratory measurements**

For lab values reported as “<x”, “<x.x”, “<x.xx” or etc. the value for analysis used will be derived by “x/2”, “x.x/2”, “x.xx/2” etc. For lab values reported as “>x”, “>x.x”, “>x.xx” or etc. the value for analysis used will be derived by increasing the last digit by 1.

#### **4.6 Blind Review**

The results of the final data assessment will be documented in the final list of important deviations, validity findings and assignment to analysis set(s). Any changes to the statistical analysis prompted by the results of the review of study data will be documented in an amendment and, if applicable, in a supplement to this SAP.

The number of positive SARS-CoV-2 tests and positive serology IgG tests and the outcomes of AEs confirming COVID-19 infections will be monitored throughout the study.

### **5. Analysis Sets**

#### **5.1 Assignment of analysis sets**

Final decisions regarding the assignment of participants to analysis sets will be made during the review of study data and documented in the final list of important deviations, validity findings and assignment to analysis set(s) (see Section 4.6).

##### **Enrolled**

All participants who sign the Informed consent form (ICF).

##### **Full analysis set (FAS)**

All participants randomly assigned to study intervention. Participants will be analyzed according to the intervention they were randomized to.

##### **Safety analysis set (SAF)**

All participants randomly assigned to study intervention and who take at least 1 tablet of study intervention. Participants will be analyzed according to the intervention they actually received. If participants received different interventions throughout the course of the study, it will be decided in the assessment meeting on a case-by-case decision which group they will be assigned to for the final analysis.

### **Per protocol set (PPS)**

All participants randomly assigned to study intervention, who have no validity findings affecting efficacy.

A list of potential validity findings will be provided in a separate important deviations and validity specifications document (Assessment Criteria and Identification Requirement (ACIR)) which will be finalized before database lock. The assignment of patients to this analysis set will be based on the assessment meetings.

The patients with invalid/missing baseline cough count measurements or only invalid/missing post-baseline cough count measurements will be excluded from the PPS.

Cough count measurements will be considered invalid if the duration of valid recording is less than 20 hours. If the treatment compliance between the previous visit and the visit of the cough count measurement is  $<80\%$  or  $>120\%$ , the measurement will also be considered invalid for the primary analysis.

Due to the repeated measurements design of the study a patient dropping out of the study may still be evaluable for efficacy and will therefore not be excluded from PPS. The minimum required treatment duration is up to including Visit 3 to allow for a valid post-baseline cough count measurement.

Participants will be analyzed according to the intervention they actually received. If participants received different interventions throughout the course of the study, they will be excluded from the PPS.

### **Listing Only Set (LOS)**

This set contains all screening failures. It will be used for listing purposes only.

The efficacy endpoints will be analyzed using the PPS, with analyses on the FAS serving as sensitivity analyses. The safety endpoints will be analyzed using the SAF. All other endpoints will be analyzed on the FAS, unless specified otherwise.

## **6. Statistical Methodology**

### **6.1 Population characteristics**

#### **6.1.1 Demographics and Baseline Characteristics**

The following demographic data and baseline characteristics will be summarized:

- Age at baseline (years);
- Age category ( $<60$  vs  $\geq 60$  years;  $<65$  vs  $\geq 65$  years);
- Sex (male vs. female)
- Race and ethnicity;
- Height (cm);
- Weight (kg) at baseline;
- BMI ( $\text{kg}/\text{m}^2$ );
- Tobacco smoking history

- Pack-years: (<10 vs ≥10 pack-years)
- Smoking status:
  - Never
  - Stopped smoking ≥ 10 years ago
  - Stopped smoking 3 to < 10 years ago
  - Stopped smoking < 3 years ago
- Alcohol consumption history

Demographic variables and baseline characteristics will be summarized using descriptive statistics and will be reported for the FAS and PPS.

Any table displaying demographics and baseline characteristics will be repeated for the following COVID-19 pandemic related subgroups:

- all randomized subjects affected by COVID-19 pandemic related study disruption
- all randomized subjects with COVID-19 adverse event and/or positive SARS-CoV-2 PCR test and/or positive serology IgG test after start of treatment

### 6.1.2 Subject Validity and Disposition

Disposition will be summarized by frequency tables. The number of subjects in SAF, FAS, PPS, the number of screening failures, patients randomized but not treated, and patients who completed study will be summarized.

Screening failures are patients who were screened, but not randomized. The reason for failed screening will be included in the summary.

A patient completed study if he/she completed all phases of the study including the last visit.

In addition, a disposition summary by study period (epoch), i.e. screening, treatment, and follow-up, will show the number of subjects completing the respective epoch and the number of subjects discontinuing it prematurely including information of the reasons for discontinuation. The table will include COVID-19 pandemic associated reasons for discontinuation, i.e. the information whether decision for discontinuation was made by the patient, the physician or was due to logistical reasons.

### 6.1.3 Medical History

Medical history findings will be summarized using Medical Dictionary for Regulatory Activities (MedDRA) terms.

Medical history of chronic cough will be analyzed using descriptive statistics based on the FAS and PPS.

### 6.1.4 Prior and Concomitant Medications

The number of participants that used prior and concomitant medication will be analyzed using frequency tables based on classified data. The classification will be done according to the WHO-DD. All prior and concomitant medications will be listed separately. The tables will display the following three categories: prior, prior/concomitant and post-treatment.

Regarding medication data collected during the study course, the following rules will be implemented:

- If the stop time of medication is before the time of the first study drug administration then medication is considered to be **prior** medication.
- If the start time of medication is before or at the time of the first study drug administration and the stop time of medication is after or at the time of the first study drug administration then the medication is considered to be **concomitant** medication.
- If the start time of medication is at or after the time of the first study drug administration and earlier than 14 days after or at the time of the last study drug administration then the medication is considered to be **concomitant** medication.
- If the start time of medication is later than 14 days after the time of the last study drug administration then the medication is considered to be **post-treatment** medication.

If time information is missing but only date information is given then classification of medication as prior or concomitant will be done by date information only. In such case, if the start day of medication is the same date as the first study drug administration, then the medication will be classified as concomitant medication.

#### 6.1.4.1 Bayer/Standardized Drug Grouping specification

In addition, the prior/concomitant medication will be displayed using the following Bayer/Standardized Drug Groupings:

- Analgesia producing opioids
- Benzodiazepines
- Corticosteroids
- Non-biologic DMARDs
- Adjuvant pain medication
  - PT: Allergic cough
  - PT: Antitussive therapy
  - PT: Atopic cough
  - PT: Cough
  - PT: Cough variant Asthma
  - PT: Habit cough
  - PT: Upper-airway cough syndrome
- Interferons
- Antihistamines and antiallergics
  - PT: Allergic cough
  - PT: Antitussive therapy
  - PT: Atopic cough
  - PT: Cough

PT: Cough variant Asthma

PT: Habit cough

PT: Upper-airway cough syndrome

- Cardiac glycosides
- Angiotensin converting enzyme (ACE) inhibitors
- Macrolides
- Direct factor Xa inhibitors
- Direct thrombin inhibitors
- Other medications for obstructive airways disorders
- Corticosteroids for obstructive airway disease
- Leukotriene receptor antagonists for obstructive airway diseases
- Monoclonal antibodies for obstructive airway diseases
- Other anti-inflammatory drugs for obstructive airway diseases
- Long acting beta agonists (LABA)
- Other bronchodilators
- Short acting beta agonist (SABA)
- Strong CYP3A inducers
- Strong CYP3A inhibitors
- Proton pump inhibitors
- Clinical BCRP substrates
- Clinical OATP1B1 substrates
- Clinical OATP1B3 substrates
- Clinical P-gp substrates

